9.1.1.4 Shipping of Specimen(s)

Slides:

Slides are to be packaged in a slide box with appropriate padding and are to be shipped out per courier service (FedEx, UPS, or comparable) to the shipping address below:

Bood (Blood):

DNA Samples (pharmacogenomic sample) need to be drawn in SST/gold top vacutainers / **serum sample** need to be drawn in purple top vacutainer. Both sample types need to be shipped on dry ice (EDTA/SST tops will not be supplied by University of Chicago and the following order numbers should be used: BD # 366643 EDTA (K2) purple top (serum samples), BD # 367987 SST 7.5 mL). The samples may be batched at institution and shipped to the address below. These samples should be shipped on Monday, Tuesday, or Wednesday and **cannot be shipped on Friday**. The shipping address is:

University of Chicago
[name]
[name]
[name]
[contact]
E-mail: [contact]

Cost of packaging and shipment cost, as well as procurement of shipping materials and courier service shipping supplies are the responsibility of each center and appropriate internal budgeting is mandatory for participation in this trial. A reference sheet outlining summarizing appropriate shipping procedures will be provided to each center.

A sample collection form is provided in **Appendix C**.

On arrival, each sample will be assigned a **Study Number**. All subsequent handling of the tissue samples will be blinded to the investigators performing various tests, except for the clinical pathologists. Only biopsy samples determined by the pathologist to contain tumour will be subjected to immunohistochemical analysis. For all immunohistochemical studies, samples will only be marked with an assigned study number. Patient name, diagnosis and other information will be unknown to the laboratory/clinical investigators involved and will be revealed only after studies are completed for further data analysis and statistics.

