9. BIOMARKER, CORRELATIVE, AND SPECIAL STUDIES

9.1 Biomarker Studies: c-MET copy number / c-MET expression (IHC)

1. Prior experience with c-MET related biomarkers

The phase II randomized study of ARQ 197 (tivantinib) in NSCLC identified c-MET copy number as a strong biomarker of ARQ 197 (tivantinib) benefit ([Sequist, Schiller et al, ESMO, 2010](#)).

The phase II randomized study of MetMab (antibody fragment against the c-MET receptor) demonstrated that benefit of MetMab was limited to tumors with c-MET expression using a standardized and centralized IHC methodology ([Spigel et al, ESMO, 2010](#)).

2. Hypothesis

Targeted agents typically only show activity/benefit in a subgroup of patients. Identification of a predictive biomarker greatly improves the effect size for a subsequent trial and increasingly is considered a requirement for drug approval.

c-MET genetic changes correlate with responsiveness in preclinical models (namely amplification, [Smolen et al, PNAS 2006](#)).

Furthermore protein expression (IHC) may be a valid marker and was shown in a clinical trial in lung cancer to correlate with benefit ([Spigel et al, ESMO 2010](#)). High expression levels are hypothesized to indicate a dependence of the tumor on the respective receptor.

3. Intended use within the proposed study

We intended to retrospectively validate the biomarkers outlined below including those suggested in the above two NSCLC studies in our patient population of HNC patients.

1. **c-MET immunohistochemistry**
2. **c-MET copy number**
3. evaluation for c-MET SNPs/mutations *
4. evaluation of copy number or mutations in c-MET related molecules including those hypothesized to cause resistance to c-MET inhibition*

5. evaluation of signatures of c-MET sensitivity/resistance using DNA and or RNA and or protein*
6. Blood will be used to extract DNA (from white cells). This DNA will be used to compare identified mutations/copy number changes

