9.1.1.2 Handling of Specimens(s)

- 10-14 slides **5 μ m** thick, cut with a clean blade (use new blade if possible or clean vigorously to avoid RNA/DNA, RNase contamination)

Slides should be usable for immunohisto-chemistry and/or DNA/RNA extraction. Review for presence of tumor is required prior to shipment at the local center.

9.1.1.3 Blood:

9.1.1.3.1 DNA Samples:

DNA Samples (pharmacogenomic sample) need to be drawn in plastic purple top vacutainers and will be used for isolation of normal DNA for validation and comparison of tumor related findings.

-> Two 7-10cc EDTA purple top tubes (plastic), BD#366643 (K2) (use of comparable tubes from the local institution is acceptable)

9.1.1.3.2 Serum Samples (pharmacogenomic sample) need to be drawn in plastic purple top vacutainers and blood for isolation of normal DNA in SST gold tops using the order numbers listed below. Use of other types of tubes needs to be confirmed with the PI/[name] (see contact info below)

- Two 10cc EDTA purple top tubes (plastic), BD#366643 (K2) (serum)

- One 7.5cc SST gold top (BD#367987) tube (blood).

1. The SST tube(s) must remain at room temperature for 30-60 minutes to clot, please invert tube 5x during this time
2. Spin tube at 1300g for 10 minutes at Room Temperature
3. Aliquot the serum evenly into cryovials (~0.5ml each)
4. Samples should be labeled with institution, protocol number (NCI 9165), patient initials, patient study ID number, and date of draw
5. Store Cryovials at -80C until shipping on dry ice at a later date

Use of other types of vacutainers needs to be confirmed with the PI/ [name] (see contact info below). Use of red top vacutainers is acceptable in place of gold top vacutainers.

Blood samples can be collected in batches, stored frozen at -80C, and subsequently shipped in batches.

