APPENDIX C

Tissue Sample Collection Form
NCI 9165: ARQ 197 (tivantinib)/Cetuximab -- HNC

Clinician/Research Nurse: Please Fill Out	
Tissue Samples	
Patient Name: _____	MRN# (if applicable): _____
Patient Protocol ID #: _____	Date Tissue Obtained: _____
Institution: _____	Attending Physician: _____
Site of Biopsy: _____	Site of Primary Tumor: _____
Did Surgical Pathology review tissue for presence of tumor (please circle)? Yes No	
Number of unstained slides (10-14 slides (5 µm thick),)	
Number of 5 µm slides: _____	
Blood collection (please check):	
Two EDTA tubes (purple top, serum), 2x10ml: ____ (e.g. BD#366643 EDTA (K2)) or similar	One SST tube 7.5ml (gold top): _____ (e.g BD#: 367987 SST, 7.5ml) or similar_ (If volume is <7.5ml provide additional tube/s)__
Date of blood draw: _____	Time of blood draw: _____
Contact Person's Phone Number and email Address at Affiliate:	

Shipment Address:

University of Chicago
[name]
[name]
[name]
[contact]
E-mail: [contact]

Please notify [name] with the tracking number once the sample was shipped:

Email: [contact]
[contact]

Disclaimer: Cost of packaging and shipment cost, as well as procurement of shipping materials and courier service shipping supplies are the responsibility of each center and appropriate internal budgeting is mandatory for participation in this trial. A reference sheet outlining summarizing appropriate shipping procedures will be provided to each center.

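### Sections 9.1.1.3.1, 9.1.1.3.2 and 9.1.1.4 and Appendix C give the purple EDTA and gold SST tubes contradictory purposes, which puts the normal-DNA sample at avoidable risk

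*Combined protocol and SAP*

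**What the plan says.** Section 9.1, item 6, states the source of the normal DNA: "Blood will be used to extract DNA (from white cells"), for comparison with changes found in the tumor. The later text of 9.1 says that this comparison is meant to separate somatic from germline changes.

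Four places then tell sites which tube to use:

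- Section 9.1.1.3.1: "DNA Samples (pharmacogenomic sample) need to be drawn in plastic purple top vacutainers and will be used for isolation of normal DNA".
- Section 9.1.1.3.2: "Serum Samples (pharmacogenomic sample) need to be drawn in plastic purple top vacutainers and blood for isolation of normal DNA in SST gold tops". Its tube list repeats the label: "Two 10cc EDTA purple top tubes (plastic), BD#366643 (K2) (serum").
- Section 9.1.1.4 (shipping): DNA samples "need to be drawn in SST/gold top vacutainers", with serum in the purple tube.
- Appendix C (the form that sites fill in): "Two EDTA tubes (purple top, serum"), and one gold SST tube with no stated purpose.

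The only processing steps are in 9.1.1.3.2 and are written for the SST tube: let it clot, spin it, then "Aliquot the serum evenly into cryovials" and freeze. No step describes what to do with an EDTA tube. The study calendar in Section 10 schedules one research blood draw, before study treatment.

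**The concern.** The same EDTA catalogue number (BD 366643) is a DNA tube in one subsection and a serum tube in the next, so a site cannot comply with both. The conflict begins inside the collection instructions, before shipping or the form is reached. It is also more than a naming slip, because the label that sends DNA to the SST tube collides with the only handling steps given, which keep serum and no cells. At stake is the patient's own normal DNA, without which a c-MET variant found in tumor tissue cannot be classed as somatic or inherited. Several sites take part and may freeze and batch their blood before shipping, so a site's misreading could recur across its patients before the central laboratory notices.

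**Working it through.** The plan states no figure on this point, so the check is a comparison of text.

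| Place | Purple EDTA | Gold SST |
|---|---|---|
| 9.1.1.3.1 | normal DNA | not mentioned |
| 9.1.1.3.2, opening sentence | serum | normal DNA |
| 9.1.1.3.2, tube list | serum | blood |
| 9.1.1.3.2, processing steps | no step | clotted, spun, serum kept |
| 9.1.1.4 | serum | DNA |
| Appendix C | serum | no purpose given |

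Step 1, labels. By section, purple is the DNA tube once (9.1.1.3.1) and the serum tube three times (9.1.1.3.2, 9.1.1.4, Appendix C). Gold is the DNA tube twice (9.1.1.3.2, 9.1.1.4). Shipping and the form do not conflict with each other on the purple tube, and the form names no DNA tube at all.

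Step 2, which mapping fits the handling. The processing steps turn the SST tube into serum aliquots and retain neither clot nor cells. Section 9.1 requires DNA from white cells. Only one mapping satisfies both: EDTA for DNA and SST for serum, as in 9.1.1.3.1.

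Step 3, routes to loss. (a) A site takes the SST as its DNA tube and follows the steps: it keeps no white cells from that tube. (b) A site takes the EDTA tubes as serum tubes and handles them by analogy with the SST: if it spins them and keeps only the supernatant, the white cells go. Normal DNA is lost only if the EDTA cells are discarded as well as the SST cells. The text instructs (a) for the SST tube. It neither instructs nor forbids (b).

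Step 4, number of tubes. Section 9.1.1.3.1 lists two EDTA tubes and 9.1.1.3.2 lists two more under the same catalogue number. Read as additive, that is 2 + 2 = 4; read as the same tubes, it is 2. Appendix C has room for two.

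Step 5, how many patients the comparison concerns. Section 9.1 describes the sequence-variant work as exploratory and centred on responders. At the design rates in 13.2 (12% and 35%, 38 patients per arm), expected responders are 0.12 × 38 + 0.35 × 38 = 4.56 + 13.30 = 17.86, about 18. If both arms respond at 12%, the figure is 2 × 4.56 = 9.12, about 9. Non-responder controls may be added, so 9 to 18 is an indication, not a ceiling.

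**The case against.** The strongest reply is that nothing tells a site to spin or discard an EDTA tube. The processing steps are addressed to the SST tube, both tube types are taken from every patient, and 9.1.1.3.2 allows blood to be frozen and shipped in batches. A site that does only what is written would spin the SST for serum and send its EDTA tubes unspun, whatever they are called, and frozen whole blood could still yield DNA. Germline DNA also does not depend on a pre-treatment time point, and patients on treatment have regular blood tests, so a failed sample could be redrawn. Finally, items 3 to 5 of Section 9.1, which include the mutation work, are optional and depend on funding.

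Most of this stands, and it limits the consequence. A reader might infer that sites following the text will lose the normal comparator in all 76 evaluable patients and that it cannot be replaced. The documents do not support that: loss needs an EDTA handling step that nobody is told to perform, a redraw is feasible, and the sequence work centres on responders.

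The reply does not remove the contradiction. Relying on sites to know the right tube means relying on them to disregard labels in three sections, one of them the form. The reference sheet promised in 9.1.1.4 is described as covering shipping, is not in the documents, and cannot be assumed to correct the labels. Item 6, the blood DNA, is not among the items marked optional.

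**Conclusion.** The tube purposes are contradictory as written, and the rule placing DNA in the SST tube cannot work with the processing steps given. This is a minor drafting fault in an operational instruction. Its likely size is small: a possible, uncertain loss of normal DNA at sites that handle EDTA tubes as serum tubes, affecting only the exploratory somatic-versus-germline comparison. The primary response comparison, PFS, OS, MET IHC and the sample size do not use this sample. Tumor MET copy number is measured on tumor DNA; only its comparison with normal DNA could be affected. The conclusion assumes that no site manual or reference sheet outside the documents already gives sites a single mapping.

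**What to change.** Use one tube-to-purpose mapping in 9.1.1.3.1, 9.1.1.3.2, 9.1.1.4 and Appendix C, matching the processing steps and the white-cell requirement: purple EDTA for normal DNA, kept as whole blood and not spun; gold SST for serum. Add one handling line for the EDTA tubes, state the purpose of the SST tube on the form, and list the two EDTA tubes once so that the number drawn is clear. The cost is a text correction in four places, with no extra samples, visits or analyses.

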9.1.1.5 Site(s) Performing Correlative Study: The University of Chicago

10. STUDY CALENDAR

Schedules shown in the Study Calendar below are provided as an example and should be modified as appropriate.

Baseline evaluations are to be conducted within 16 days prior to start of protocol therapy. Scans and x-rays must be done ≤ 4 weeks prior to the start of therapy. In the event that the patient's condition is deteriorating, laboratory evaluations should be repeated within 48 hours prior to initiation of the next cycle of therapy.

	Pre-Study	Wk 1	Wk 2	Wk 3	Wk 4	Wk 5	Wk 6	Wk 7	Wk 8	Wk 9	Wk 10	Wk 11 and every 2 weeks thereafter	Wk 12	Off Study ^c
ARQ 197 (tivantinib)		A------(given twice daily)-----A												
Cetuximab		B		B		B		B		B		B		
Informed consent	X													
Demographics	X													
Medical history	X													
Concurrent meds	X	X-----X												
Physical exam	X	X		X		X				X		every 4 wks		X
Vital signs	X	X		X		X				X		x		X
Height	X													
Weight	X	X		X		X		X		X		x		X
Performance status	X	X		X		X				X				X
CBC w/diff, plts	X	X	X	X	X	X	X	X	X	X	X	X	X	X
Research Blood draw	X													
Serum chemistry ^a	X	X	X	X	X	X	X	X	X	X	X	X	X	X
EKG (at baseline then as indicated)	X	X												
Adverse event evaluation		X-----X												X
Tumor measurements	X	Tumor measurements are repeated every 8 weeks. Documentation (radiologic) must be provided for patients removed from study for progressive disease.												X
Radiologic evaluation	X	Radiologic measurements should be performed every 8 weeks.												X
B-HCG	X ^b													
Unstained slides of tumor	X													

A: *ARQ 197 (tivantinib)*: Dose as assigned; *po twice daily*
B: *Cetuximab*: Dose as assigned; *every two weeks*
a: Albumin, alkaline phosphatase, total bilirubin, bicarbonate, BUN, calcium, chloride, creatinine, glucose, LDH, phosphorus, potassium, total protein, SGOT [AST], SGPT [ALT], sodium, magnesium
b: Serum pregnancy test (women of childbearing potential).
c: Off-study evaluation.
Starting week 5 – MD visits are only required every 4 weeks, unless more frequent visits are medically indicated.

11. MEASUREMENT OF EFFECT

11.1 Antitumor Effect – Solid Tumors

For the purposes of this study, patients should be reevaluated for response every 8 weeks. In addition to a baseline scan, confirmatory scans should also be obtained 4-6

weeks following initial documentation of objective response. In the case of SD, follow-up measurements must have met the SD criteria at least once after study entry at a minimum interval of 12 weeks

Response and progression will be evaluated in this study using the new international criteria proposed by the revised Response Evaluation Criteria in Solid Tumors (RECIST) guideline (version 1.1) (*Eisenhauer EA et al, Eur J Ca, 2009*). Changes in the largest diameter (unidimensional measurement) of the tumor lesions and the shortest diameter in the case of malignant lymph nodes are used in the RECIST criteria.

11.1.1 Definitions

Evaluable for toxicity. All patients will be evaluable for toxicity from the time of their first treatment with ARQ 197 (tivantinib)/ cetuximab.

Evaluable for objective response. Only those patients who have measurable disease present at baseline, and have **received any study drug**, and have had their disease re-evaluated will be considered evaluable for response. These patients will have their response classified according to the definitions stated below (see 13.5.2). (Note: Patients who exhibit objective disease progression prior to the end of cycle 1 will also be considered evaluable.).

Evaluable Non-Target Disease Response. Patients who have lesions present at baseline that are evaluable but do not meet the definitions of measurable disease, have **received any study drug**, and have had their disease re-evaluated will be considered evaluable for non-target disease. The response assessment is based on the presence, absence, or unequivocal progression of the lesions.

11.1.2 Disease Parameters

Measurable disease. Measurable lesions are defined as those that can be accurately measured in at least one dimension (longest diameter to be recorded) as ≥ 20 mm by chest x-ray, as ≥ 10 mm with CT scan, or ≥ 10 mm with MRI, or calipers by clinical exam. All tumor measurements must be recorded in millimeters (or decimal fractions of centimeters).

Note: Tumor lesions that are situated in a previously irradiated area might or might not be considered measurable. If such lesions show evidence of tumor progression / have known disease they should be included and measurement attempted.

Malignant lymph nodes. To be considered pathologically enlarged and measurable, a lymph node must be ≥ 15 mm in short axis when assessed by CT scan (CT scan slice thickness recommended to be no greater than 5 mm). At baseline and in follow-up, only the short axis will be measured and followed.

Non-measurable disease. All other lesions (or sites of disease), including small lesions (longest diameter <10 mm or pathological lymph nodes with ≥ 10 to <15 mm short axis), are considered non-measurable disease. Bone lesions, leptomeningeal disease, ascites, pleural/pericardial effusions, lymphangitis cutis/pulmonitis, inflammatory breast disease, and abdominal masses (not followed by CT or MRI), are considered as non-measurable.

Note: Cystic lesions that meet the criteria for radiographically defined simple cysts should not be considered as malignant lesions (neither measurable nor non-measurable) since they are, by definition, simple cysts.

‘Cystic lesions’ thought to represent cystic metastases can be considered as measurable lesions, if they meet the definition of measurability described above. However, if non-cystic lesions are present in the same patient, these are preferred for selection as target lesions.

Target lesions. All measurable lesions up to a maximum of 2 lesions per organ and 5 lesions in total, representative of all involved organs, should be identified as **target lesions** and recorded and measured at baseline. Target lesions should be selected on the basis of their size (lesions with the longest diameter), be representative of all involved organs, but in addition should be those that lend themselves to reproducible repeated measurements. It may be the case that, on occasion, the largest lesion does not lend itself to reproducible measurement in which circumstance the next largest lesion which can be measured reproducibly should be selected. A sum of the diameters (longest for non-nodal lesions, short axis for nodal lesions) for all target lesions will be calculated and reported as the baseline sum diameters. If lymph nodes are to be included in the sum, then only the short axis is added into the sum. The baseline sum diameters will be used as reference to further characterize any objective tumor regression in the measurable dimension of the disease.

Non-target lesions. All other lesions (or sites of disease) including any measurable lesions over and above the 5 target lesions should be identified as **non-target lesions** and should also be recorded at baseline. Measurements of these lesions are not required, but the presence, absence, or in rare cases unequivocal progression of each should be noted throughout follow-up.

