2. BACKGROUND

2.1 Study Disease

Head and Neck squamous cell carcinoma (HNSCC) is the 6th most common cause of cancer death worldwide with more than 600,000 cases annual. In the United States, approximately 40,500 new HNSCC cases and 11,000 deaths were expected in 2006. HNSCC results in significant morbidity because major vital functions such as nutrition, respiration and communication are impaired.

Approximately two thirds of patients with HNSCC will present with locoregional disease and despite aggressive local therapy, close to than half will succumb to recurrent and/or metastatic disease. If untreated, the median survival of patients with metastatic disease is dismal and on the order of 4 months (*Ang, Berkey et al. 2002*).

In patients with recurrent or metastatic HNSCC, the only therapeutic options are usually palliative consisting of systemic chemotherapy and the EGFR inhibitor cetuximab (*Vermorken, Mesia et al. 2008*). Median survival is estimated at 10.1 months using a combination of cisplatin/5-FU/cetuximab. Cytotoxic chemotherapy

can have significant toxicities, consisting of bone marrow suppression, nausea/vomiting, rash, hand-foot syndrome, and many others.

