3. PATIENT SELECTION

3.1 Eligibility Criteria

Inclusion Criteria:

- 3.1.1 Histologically / cytologically confirmed diagnosis of squamous cell carcinoma of Head and Neck origin not amenable to curative intent therapy. Both HPV(+) and HPV(-) are eligible, but status has to be known prior to randomization (although not required for consenting). Any type of tissue based HPV assessment is acceptable (e.g. p16 IHC or HPV ISH). If local HPV testing is not available slides can be sent to the University of Chicago for HPV testing. Please note that p16 IHC is generally only considered to be accurate for oropharyngeal tumors.
- 3.1.2 Presence of measurable lesions (as per RECIST 1.1). Generally a ≥ 10 mm tumor lesion (in the longest diameter by CT scan) or a Lymph node ≥ 15 mm (short axis) is considered measurable disease when evaluated by CT scan (with a slice thickness no greater than 5 mm). Please review full RECIST 1.1 criteria ([Eisenhauer EA et al, Eur J Ca, 2009](#)) as well as Section 11 for further details.
- 3.1.3 Availability of tissue (10 tumor containing FFPE slides/sections)
- 3.1.4 ECOG performance status of 0, 1 (see Appendix A).
- 3.1.5 Patients who have received cetuximab or another inhibitor of EGFR in the curative intent treatment setting (e.g. with radiation or during induction chemotherapy (prior to definitive, curative intent therapy)) are eligible for the study.
- 3.1.6 Age ≥ 18 years.

Because no dosing or adverse event data are currently available on the use of ARQ 197 (tivantinib) in patients < 18 years of age, children are excluded from this study, but will be eligible for future pediatric trials.

- 3.1.7 Life expectancy of greater than 8 weeks.
- 3.1.8 Patients must have normal organ and marrow function as defined below:

- hemoglobin	≥ 9.0 g/dL
- leukocytes	$\geq 3,000$ /mcL
- absolute neutrophil count	$\geq 1,500$ /mcL
- platelets	$\geq 100,000$ /mcL
- total bilirubin	≤ 1.5 X institutional upper limit of normal
- AST(SGOT)/ALT(SGPT)	≤ 2.5 X institutional upper limit of normal
- serum creatinine	≤ 1.5 X institutional upper limit of normal

OR

– creatinine clearance ≥ 60 mL/min/1.73 m² for patients with creatinine levels above institutional normal.

- 3.1.9 Patients must be able to swallow ARQ 197 (tivantinib) by mouth, unless adequate data about administration by G-tube becomes available. Tablets may be crushed, but must be taken orally.

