3.2 Exclusion Criteria

- 3.2.1 Patients who have had chemotherapy or radiotherapy within 2 weeks (6 weeks for nitrosoureas or mitomycin C) prior to entering the study or those who have not recovered from adverse events due to agents administered more than 2 weeks earlier.
- 3.2.2 Nasopharyngeal tumors that show lymphoepithelioma histology
- 3.2.3 Patients who have received more than 2 prior cytotoxic treatments in the palliative treatment setting are ineligible.
- 3.2.4 Patients who have received prior treatment with an EGFR or MET inhibitor in the palliative treatment setting are ineligible
- 3.2.5 Patients with known, active brain metastases should be excluded from this clinical trial because of their poor prognosis and because they often develop progressive neurologic dysfunction that would confound the evaluation of

neurologic and other adverse events. Patients with treated brain metastases stable for ≥ 12 weeks are eligible. Use of corticosteroids (for patients with brain metastasis and other indications for corticosteroid use) is acceptable on a low maintenance or tapering dose schedule.

- 3.2.6 History of allergic reactions attributed to compounds of similar chemical or biologic composition to AR 197 (tivantinib) or cetuximab.
- 3.2.7 Concurrent life-threatening diseases: Patients with diseases which with reasonable certainty do not limit life expectancy to 12 months or less are eligible. Assessment of such concurrent illnesses should be by the Principal Investigator
- 3.2.8 Uncontrolled intercurrent illness including, but not limited to, ongoing or active infection, symptomatic congestive heart failure, unstable angina pectoris, cardiac arrhythmia, or psychiatric illness/social situations that would limit compliance with study requirements.
- 3.2.9 Pregnant women are excluded from this study because ARQ 197 (tivantinib) is a tyrosine kinase inhibitor with the potential for teratogenic or abortifacient effects. Because there is an unknown but potential risk for adverse events in nursing infants secondary to treatment of the mother with ARQ 197 (tivantinib), breastfeeding should be discontinued if the mother is treated with ARQ 197 (tivantinib).
- 3.2.10 Concurrent use of warfarin (therapeutic use) is allowed, but requires close monitoring of PT/INR (See Section 5.2)

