11.1.4 Response Criteria

11.1.4.1 Evaluation of Target Lesions

Complete Response (CR): Disappearance of all target lesions. Any pathological lymph nodes (whether target or non-target) must have reduction in short axis to <10 mm.

Partial Response (PR): At least a 30% decrease in the sum of the diameters of target lesions, taking as reference the baseline sum diameters.

Progressive Disease (PD): At least a 20% increase in the sum of the diameters of target lesions, taking as reference the smallest sum on study (this includes the baseline sum if that is the smallest on study). In addition to the relative increase of 20%, the sum must also demonstrate an absolute increase of at least 5 mm. (Note: the appearance of one or more new lesions is also considered progressions).

Stable Disease (SD): Neither sufficient shrinkage to qualify for PR nor sufficient increase to qualify for PD, taking as reference the smallest sum diameters while on study.

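### The rule for previously irradiated lesions can be read to admit a target lesion on known disease alone, so radiation regression could count toward response; an explicit condition fixes this cheaply.

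*Combined protocol and SAP*

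**What the plan says.** The note under measurable disease in section 11.1.2 has two sentences. The first is permissive: "Tumor lesions that are situated in a previously irradiated area might or might not be considered measurable". The second gives the working rule: "If such lesions show evidence of tumor progression / have known disease they should be included and measurement attempted".

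The other provisions that bear on it are these:

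- **Target selection (11.1.2).** The pool is "All measurable lesions up to a maximum of 2 lesions per organ and 5 lesions in total", chosen by size, representativeness and reproducibility. Irradiated lesions are not treated separately.
- **Radiotherapy washout (3.2.1).** The exclusion covers "Patients who have had chemotherapy or radiotherapy within 2 weeks (6 weeks for nitrosoureas or mitomycin C) prior to entering the study".
- **Baseline imaging (section 10, repeated in 11.1.3).** "Scans and x-rays must be done ≤ 4 weeks prior to the start of therapy".
- **Partial response (11.1.4.1).** "At least a 30% decrease in the sum of the diameters of target lesions", measured against the baseline sum.
- **Prior treatment.** Section 3.1.5 admits patients given an EGFR inhibitor with curative intent, "e.g. with radiation or during induction chemotherapy". Section 2.1 says of locoregional presentations that "despite aggressive local therapy, close to than half will succumb to recurrent and/or metastatic disease".

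Section 3.1.2 defines measurable disease by lesion size and refers the reader to the full RECIST 1.1 criteria. No section of the protocol itself requires progression after radiation before an irradiated lesion may be a target.

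**The concern.** A tumor lesion under consideration as a target is ordinarily already known disease. If the slash means *or*, the second condition swallows the first, and almost any irradiated lesion of sufficient size qualifies. If it means *and*, the second condition adds little, because a progressing lesion is already known disease. On either reading the progression limb has no time reference, so progression that led to the radiation would satisfy it.

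A lesion irradiated shortly before entry may still be shrinking when the baseline scan is taken. If it makes up much of the target sum, that shrinkage can help the patient across the 30% threshold without any effect of study drug. The same measurements feed the primary response rate, the 8-week change in tumor burden (13.4) and the futility look, which compares observed response rates (13.2). Different sites could also settle the ambiguity differently, in an open-label trial whose randomization is stratified by HPV status only.

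**Working it through.** **Timing.** Radiation may end 14 days before entry. If therapy starts at entry, a baseline scan taken 28 days before therapy predates the end of radiation by up to 28 − 14 = 14 days. A scan taken after radiation removes that overlap, but not regression that continues after the scan.

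**The plan's own sample size (13.2).** Inputs: p1 = 0.12, p2 = 0.35, difference d = 0.23, one-sided alpha 0.10 (z = 1.2816), power 80% (z = 0.8416), continuity-corrected chi-square. The mean rate is 0.235.

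- Uncorrected: n0 = [1.2816 × √(2 × 0.235 × 0.765) + 0.8416 × √(0.12 × 0.88 + 0.35 × 0.65)]² / 0.23² = (0.7684 + 0.4857)² / 0.0529 = 29.7.
- Corrected: n = (n0/4) × [1 + √(1 + 4/(n0 × d))]² = (29.7/4) × (1 + 1.259)² = 37.9, so 38 per arm.

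The stated 38 per arm is reproduced. Enumerating every pair of binomial counts for the corrected test at 38 per arm gives an exact power of 81.6%.

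**Sensitivity to carry-over.** Let f be the share of would-be non-responders, equal in both arms, who are scored as responders because of radiation regression. The documents give no value, so f is an assumption. Each rate becomes p + f(1 − p), and the difference becomes 23 × (1 − f) points. For f = 5%, control is 0.12 + 0.05 × 0.88 = 0.164 and combination is 0.35 + 0.05 × 0.65 = 0.3825.

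| f | Control | Combination | Difference (points) | Exact power, 38 per arm |
|---|---|---|---|---|
| 0% | 12.00% | 35.00% | 23.00 | 81.6% |
| 1% | 12.88% | 35.65% | 22.77 | 80.1% |
| 2% | 13.76% | 36.30% | 22.54 | 78.6% |
| 5% | 16.40% | 38.25% | 21.85 | 74.0% |
| 10% | 20.80% | 41.50% | 20.70 | 66.4% |

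Most of the loss comes from the higher variance at higher rates; the difference itself shrinks little. In patients, f = 5% means about 38 × 0.044 = 1.7 spurious responses in the control arm and 38 × 0.0325 = 1.2 in the combination arm.

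**False-positive risk.** With the same true rate in both arms, set at the control rate for f from 0 to 20% (12.0% to 29.6%), the exact one-sided type I error of the corrected test runs from 5.0% to 6.3%, below the nominal 10%.

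**The case against.** The strongest reply is that the text is softer and the scenario rarer than the concern suggests. The note says *should*, after a sentence that leaves measurability open, and progression is the criterion it names first. In an irradiated field, known disease may mean tumor known to be present as opposed to scar, which gives the phrase some content. Section 13.1 says that patients will typically have had first-line cytotoxic chemotherapy, and the radiation in 3.1.5 was given with curative intent, so much of it may lie well before entry. A spurious response also needs a 30% fall in the whole target sum, with no new lesion and no non-target progression. At f = 1% the planned 80% is still met. Sections 3.1.2 and 11.1 also invoke RECIST 1.1, whose text is not reproduced here.

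Much of this stands. It limits how often the problem would arise, but it does not settle what the rule means, and a site would follow the protocol's own sentence on irradiated lesions.

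A reader might infer more than the documents support:

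- *That inclusion on known disease is mandatory, or that progression is expressly waived.* The wording is ambiguous and says neither.
- *That the population is heavily irradiated.* Sections 2.1 and 3.1.5 make irradiated lesions foreseeable, but no share is given.
- *That the result is biased toward the combination.* Equal carry-over raises both rates and costs power. Chance imbalance is possible, since prior radiation is not a stratification factor, but no direction is implied.
- *That the control rate could no longer be compared with the 10–13% in 13.2.* The documents do not say how irradiated lesions were handled in the historical cetuximab data, and the primary comparison is with a concurrent randomized control.

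**Conclusion.** The point holds as a cheap improvement to the definition of the primary endpoint. On its most natural reading, 11.1.2 lets an irradiated lesion be a target on known disease alone, and nothing else in the protocol's own text requires progression since radiation. The washout and the baseline-scan window leave room for residual radiation effect to be counted.

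The size is unknown. If f is equal in both arms, the loss of exact power is about 1.5 points at f = 1%, 3 at 2%, 7.6 at 5% and 15 at 10%, with response rates inflated in both arms. These figures rest entirely on the assumed f and on equal carry-over. The sample size of 38 per arm reproduces and need not change.

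**What to change.** In 11.1.2, replace the second sentence of the note with: *A lesion in a previously irradiated area may be selected as a target lesion only if progression in that lesion has been documented since completion of radiation; otherwise record it as non-target.* In section 10 and 11.1.3, add that the baseline tumor scan must be done after radiation is completed.

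The cost is a sentence in each place and an item on the baseline lesion form. The downside is that a few patients whose only measurable lesion is irradiated and has not progressed would have no target lesion. They would meet the size criterion in 3.1.2 but could not be scored for partial response, so the plan should say how they are handled. Whether 3.1.2 should also be narrowed is a trade-off against accrual for the sponsor to decide.
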